11.7 Cardiac Doppler or Multi Gated Acquisition Scan

The Left ventricular ejection fraction (LVEF) is collected over time at selected visits. It will be measured by either echocardiography (ECHO), Multi Gated Acquisition Scan (MUGA) or MRI. Recorded values of LVEF and change from baseline values will be summarized by treatment group and by visit.

Corresponding listing will be provided for LVEF data.

11.8 ECOG Performance Status

The eastern cooperative oncology group (ECOG) scale is used to assess how the disease affects subjects' daily activities. ECOG is classified into 6 categories:

- 0 = fully active, able to carry on all pre-disease performance without restriction;
- 1 = restricted in physically strenuous activity but ambulatory and able to carry out work of a light or sedentary nature, e.g., light housework, office work;
- 2 = ambulatory and capable of all self-care but unable to carry out any work activities, up and about more than 50% of waking hours;
- 3 = capable of only limited self-care, confined to bed or chair more than 50% of waking hours;
- 4 = completely disabled, cannot carry on any self-care, totally confined to bed or chair;
- 5 = dead.

The ECOG status at screening visit was summarized in the demographic table. A listing has been provided for ECOG data. No ECOG summary will be presented in the final CSR.

11.9 Antidrug Antibody Testing

The anti-luspatercept antibody test is conducted over time. There are 4 ADA parameters: [REDACTED]. Titer information is collected [REDACTED]. Specificity test, Nab and titer data are only available for subjects who are positive [REDACTED].

To evaluate the treatment-emergent ADA level, the number and percentage of positive ADA result has been provided by parameter. The summary is broken down by ADA positive categories

████████████████████ within each treatment: “Preexisting”, “Treatment-Emergent” and “Positive total”. The “Positive total” category is the sum of “Preexisting” and “Treatment-Emergent”. A subject is counted as ‘Treatment-Emergent’ if there is a positive post-baseline sample while the baseline sample is ADA negative, or there is a positive post-baseline sample with a titer \geq 4-fold of the baseline titer while the baseline sample is ADA positive. A subject is counted as ‘Preexisting’ if the baseline sample is ADA positive and the subject is not qualified for ‘Treatment-Emergent’.

A separate table summarizes the ADA titer information. For placebo group, only subjects with ADA sample collected are included; for luspatercept group, only subjects who are positive ██████████ are included. The median, min and max value are provided for ADA titer by treatment group and visit. Specifically, the titer summary for luspatercept subjects is split to: “Preexisting”, “Treatment-Emergent” and “positive total” groups as defined above. Corresponding listing are provided to support the table.

[figure not shown]
Additionally, a bar plot has been provided for subject’s ADA status (“Preexisting”, “Treatment-Emergent” and “Negative”). Percent of subjects within each category has been displayed by treatment group.

Since the ADA sample is not collected during the Open Label phase, there will be no additional ADA analysis in the final CSR.

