**Table 2: Study Endpoints**

Endpoint	Name	Description	Time of Endpoint Measurement			Timeframe
			24 weeks	48 weeks	Long -Term	
Primary Endpoint	
 
Proportion of subjects with hematological improvement, defined as <math>\geq 33\%</math> reduction from baseline in RBC transfusion burden with a reduction of at least 2 units from Week 13 to Week 24 compared to the 12-week interval prior to randomization for luspatercept plus BSC versus placebo plus BSC.
 
	Number of RBC units transfused from Week 13 to Week 24, and in the 12 weeks prior to randomization	X	-	-	12 weeks prior to randomization; Week 13-Week 24.
Safety Endpoints	
 
Safety, including:                             
 
Type, frequency, and severity of adverse events and relationship to luspatercept (per NCI CTCAE version 4.0)
 
 
 
	Frequency/severity of adverse events	X	X	X	All AE Dose 1 Day 1 through up to 9 weeks post last dose. Only related AEs from week 9 until End of Study.
	
 
Frequency of antidrug antibodies [REDACTED]
 
	ADA measurements; [REDACTED]	X	X	X	Dose 1 Day 1 through up to 2 years
Secondary Efficacy Endpoints	
 
Proportion of subjects with hematological improvement, defined as <math>\geq 33\%</math> reduction from baseline in RBC transfusion burden with a reduction of at least 2 units from Week 37 to Week 48 compared to the 12-week interval prior to randomization for luspatercept plus BSC versus placebo plus BSC.
 
	Number of RBC units transfused from Week 37 to Week 48, and in the 12 weeks prior to randomization	-	X	-	12 weeks prior to randomization; Week 37-Week 48

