-  Day 22 post-last dose corresponds to the end of Treatment Period.
-  Calculated doses requiring reconstituted volume greater than 1 mL should be divided equally into two syringes and injected into two separate sites – same anatomical location but opposite side of the body (example left thigh and right thigh). In case of 2 simultaneous injections, the injection sites must be different. In case of dose delays refer to Section 6.2.1 and Section 6.3.1. Only for Dose 1 Day 1, IP administration should be at the end of the Screening/Run-in period, which is at least 12 weeks.
-  Assessments to be performed if the subject is in this study at Week 96, not applicable if subject does not enter into the LTTP.
-  During the Long-term Treatment Period, PK and ADA samples will be collected every 6 doses. The maximum ADA monitoring period will be two years from dose 1 day 1 of the double-blind Treatment Period. During the Open-label Phase: for placebo-cross-over subjects, if positive at unblinding, continue every 6 doses up to 2 years from Dose 1 Day 1 of the double-blind Treatment Period; for subjects continuing treatment with luspatercept, only if positive at unblinding, every 6 doses up to 2 years from Dose 1 Day 1 of the double blinded treatment period. During the Post-Treatment Follow-Up : Before unblinding, ADA monitoring, every 24 weeks (post last dose), at post-treatment follow-up visits will continue for up to two years from Dose 1 Day 1 of the double-blind Treatment Period. After unblinding, ADA monitoring, every 24 weeks (post last dose), at all post-treatment follow-up visits will continue only if subjects' last available ADA is positive and have not reached the 2-year maximum limit for ADA monitoring. ADA/PK sampling per Investigator's or Sponsor's discretion is allowed and should be recorded as unscheduled visit.
-  During the Long-term Treatment Period these parameters should be measured by Central Lab. Data to be entered in the eCRF.
-  MRI for LIC, myocardial iron (T2\*) and for spleen volume can be performed on one MRI acquisition if possible.

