### 6.9. Anti-Drug Antibody

Serum samples will be collected for assessment of anti-drug antibodies (ADA) in all subjects. The maximum ADA monitoring period will be two years from dose 1 day 1 of double-blind Treatment Period. An additional blood draw is not needed for the anti-luspatercept antibody test.

The anti-luspatercept antibody test will be conducted for the following visits utilizing the PK samples obtained at the same visit:

- Treatment Period: Doses 1 to 16: Predose (Dose 1 Day 1, must be collected before the first dose), Dose 2 Day 1, Dose 4 Day 1, Dose 6 Day 1, Dose 8 Day 1, Dose 12 Day 1, Dose 16 Day 1.
- Long-term Treatment Period: every 6 doses.
- Open Label Phase: for placebo-cross-over subjects, only if positive at unblinding, continue every 6 doses up to 2 years from Dose 1 Day 1 of the double-blind Treatment Period. For subjects continuing treatment with luspatercept, only if positive at unblinding, every 6 doses up to 2 years from Dose 1 Day 1 of the double blinded treatment period..
- Post-treatment Follow-up (starting at Follow-up Week 9):
  - Before unblinding: every 24 weeks post last dose until the unblinding for up to two years from Dose 1 Day 1 of double-blind Treatment Period.
  - After unblinding, ADA monitoring every 24 weeks post last dose, only if subjects' last available ADA is positive and they have not reached the 2-year maximum limit for ADA monitoring.

ADA/PK sampling per Investigator's or Sponsor's discretion is allowed and should be recorded as an unscheduled visit.

CCI

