- For RBC transfusion related efficacy endpoints summary beyond the 48-week double-blinded

treatment period, the 12-week interval is defined as:

Week 49 - 60 interval: from Day 338 to Day 421;
Week 61 - 72 interval: from Day 422 to Day 505;
Week 73 - 84 interval: from Day 506 to Day 589;
Week 85 - 96 interval: from Day 590 to Day 673;
Week 97 - 108 interval: from Day 674 to Day 757;
Week 109 - 120 interval: from Day 758 to Day 841;
Week 121 - 132 interval: from Day 842 to Day 925;
Week 133 - 144 interval: from Day 926 to Day 1009;
Week 145 - 156 interval: from Day 1010 to Day 1093;
Week 157 - 168 interval: from Day 1094 to Day 1177;
Week 169 - 180 interval: from Day 1178 to Day 1261;
Week 181 - 192 interval: from Day 1262 to Day 1345;
Week 193 - 204 interval: from Day 1346 to Day 1429;
Week 205 - 216 interval: from Day 1430 to Day 1513;
Week 217 - 228 interval: from Day 1514 to Day 1597.

All the data collected up to 11MAY2018 were used for summary in the primary CSR. The final database will be locked when everyone rolls over to a long-term follow-up study. All data collected up to the time of every subject rolling over to the long term follow up study will be used for summary. Data selection rules will be applied in each summary panel as needed, please refer to relevant sections for details.

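### SAP 11.9 drops ADA from the final CSR on the ground that none is collected in open label, but the protocol schedules it there for subjects positive at unblinding

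*SAP*

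**What the plan says.** SAP 11.9 describes the ADA summaries as already provided and closes the topic: "Since the ADA sample is not collected during the Open Label phase, there will be no additional ADA analysis in the final CSR". In line with that, SAP 3.2.1 lists safety and immunogenicity as completed, while SAP 3.2.2 carries forward safety alone. SAP 4.2.4.1 has an ADA endpoint and 4.2.4.2 does not. The introduction to SAP Section 11 nevertheless names ADA testing as part of the safety analysis. It also sets a default that safety summaries include records collected after the primary lock unless otherwise specified.

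Protocol Table 2 lists ADA frequency as a safety endpoint, ticked for 24 weeks, 48 weeks and long-term, with time frame "Dose 1 Day 1 through up to 2 years". Protocol 6.9 sets the limit: "The maximum ADA monitoring period will be two years from dose 1 day 1 of double-blind Treatment Period". Its open-label rules are:

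- Continuing subjects: "For subjects continuing treatment with luspatercept, only if positive at unblinding, every 6 doses up to 2 years from Dose 1 Day 1".
- Cross-over subjects: "for placebo-cross-over subjects, only if positive at unblinding, continue every 6 doses up to 2 years from Dose 1 Day 1".

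For follow-up it says: "After unblinding, ADA monitoring every 24 weeks post last dose, only if subjects' last available ADA is positive", subject to the same 2-year limit. Before unblinding, follow-up sampling is every 24 weeks without that condition. Table 3 marks ADA in both open-label columns, footnote 10 repeats the rule, and Protocol 6.4 lists ADA, where applicable, among the open-label procedures.

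**The concern.** The only reason the SAP gives for stopping ADA analysis is a statement about data collection that the current protocol contradicts. Even if the statement were true, it concerns one study phase, while the conclusion drawn from it covers every ADA sample after the primary cutoff.

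Protocol 1.2.1.4 says antidrug antibodies can be associated with faster drug clearance and with hypersensitivity. After unblinding, the scheduled samples come from subjects already known to be positive. Those samples show whether an antibody response persists, disappears or rises in titre. Under SAP 11.9 a 4-fold titre rise reclassifies a subject from pre-existing to treatment-emergent, so the omitted samples could change a reported category as well as a listing.

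**Working it through.** No sample size, error rate or test is involved, so there is no plan figure to reproduce. The check sets the sampling rules against the SAP's reason and then sizes the remaining window.

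**1. Which samples after the cutoff does the reason cover?**

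SAP 5.1 fixes the cutoff: "All the data collected up to 11MAY2018 were used for summary in the primary CSR".

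| ADA sample after 11 May 2018 | Protocol rule (6.9, Table 3, footnote 10) | SAP 11.9 reason |
|---|---|---|
| Long-term Treatment Period, up to unblinding | Every 6 doses, regardless of ADA status | Does not apply: not open label |
| Follow-up, before unblinding | Every 24 weeks, regardless of ADA status | Does not apply |
| Open-label Phase | Every 6 doses, only if positive at unblinding | Contradicted |
| Follow-up, after unblinding | Every 24 weeks, only if last ADA was positive | Does not apply |
| Unscheduled | At investigator or sponsor discretion | Contradicted in open label; otherwise does not apply |

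The scheduled rows all stop at 2 years from Dose 1 Day 1 of the double-blind period.

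**2. How long is the gap between cutoff and unblinding?**

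SAP Section 2 says the primary SAP was signed on 19 June 2018, before the primary lock. Protocol 9.9.1.1 puts unblinding at the lock. From 11 May to 19 June is 20 + 19 = 39 days, so on that reading the gap is at least 39 days. SAP 4.1 ties unblinding to the last subject reaching 48 weeks, which could make it shorter. Long-term samples fall in the gap only if long-term dosing continued after the cutoff.

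**3. How much of the 2-year window was left at the cutoff?**

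Inputs: 48 weeks = 336 days; 2 years = 730 days; 6 doses at 3-week intervals = 18 weeks = 126 days. The date of the last first dose is not given, so I assume the last subject had exactly 48 weeks at the cutoff.

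- Last first dose: 11 May 2018 − 336 days = 9 June 2017.
- End of that subject's window: 9 June 2017 + 730 days = 9 June 2019.
- Window left: 730 − 336 = 394 days; 394 / 7 = 56.3 weeks.
- Scheduled samples: 394 / 126 = 3.1, so about 3. With no dose delays these are Doses 22, 28 and 34, given (dose − 1) × 3 weeks after Dose 1, at Weeks 63, 81 and 99.

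This is the maximum. The amendment rationale reports 281 subjects randomized by 4 April 2017. A subject first dosed on that date had 402 days (57.4 weeks) at the cutoff and 730 − 402 = 328 days (46.9 weeks) left. Subjects first dosed on or before 11 May 2016 had the whole window inside the primary CSR; their number is not given.

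**4. What could the omitted samples show?**

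- In subjects positive at unblinding: persistence, loss, and titre change including the 4-fold rule.
- In subjects negative at unblinding: nothing from scheduled samples after unblinding, because the protocol schedules none. New positives could arise only before unblinding or in unscheduled samples.
- In cross-over subjects negative at unblinding: no scheduled test at all after their first luspatercept dose.

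**The case against.** The strongest reply is that the scope was chosen openly. ADA is listed as completed, is not extended, is descriptive, and no test depends on it. SAP Section 2 also limits the final analysis to selected key endpoints. That would carry weight if SAP 11.9 rested on selection, but it rests on non-collection, and that premise conflicts with the protocol.

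A second reply is that the SAP was signed in March 2021, after the 2-year window estimated here had closed. Its authors may have known that no qualifying samples were taken. That is possible: the documents give neither the number positive at unblinding nor the number of open-label samples, and the loss could be zero. If so, the text should say so, because the protocol required sampling in anyone who qualified.

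A reader might go further and infer that the trial gathers second-year immunogenicity data on everyone and never analyses it. The documents do not support that:

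- Results up to 11 May 2018, including second-year ones, were in the primary CSR.
- Two years is a ceiling on monitoring, so there is no fixed 2-year endpoint being cut short.
- For ADA-negative subjects it is the protocol that ends scheduled sampling at unblinding.

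**Conclusion.** The point holds in a limited form. The SAP cancels further ADA analysis for a reason the protocol contradicts, and the cancellation reaches samples the reason does not cover. That runs against the SAP's own default for safety data and against Protocol 9.9.1.2, which includes safety endpoints in the final analyses.

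The 56 weeks is an upper limit for the last-dosed subject and rests on the assumed 48 weeks at the cutoff. Beyond unblinding it concerns scheduled samples in ADA-positive subjects only, so it should not be read as a year of lost data across the trial. Neither the number of subjects affected nor whether the samples are in the database can be determined from the documents.

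**What to change.** Replace the closing sentence of SAP 11.9.

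- **If samples exist:** update the pre-existing / treatment-emergent table, the titre summary and the listing with every ADA result after 11 May 2018 that falls within 2 years of double-blind Dose 1 Day 1. Include long-term, open-label, follow-up and unscheduled samples. Add a listing of persistence in positive subjects, and restore ADA in SAP 3.2.2 and 4.2.4.2.
- **If none were taken:** say so, give the reason, and record the departure from Protocol 6.9.

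In either case, state that cross-over subjects negative at unblinding had no scheduled ADA test after first luspatercept exposure, so no ADA rate is claimed for them. This matters because SAP Section 11 plans safety summaries for groups that contain these subjects.

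The cost is a re-run of existing descriptive outputs plus one listing, or a short statement if there is nothing to report. No new sampling is needed, and no hypothesis test or error rate changes.

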11.10 Pregnancy Test and Menstrual Status for Female Subjects

The number and percentage of the subjects for each pregnancy test result category (i.e., positive, negative) will be presented by treatment group. A subject is counted as ‘positive’ if there is any positive result captured after first dose date, a subject is counted as ‘negative’ if there is no positive result captured after first dose date.

The pregnancy test along with menstrual status will be provided in a listing.

13. PK ANALYSIS

This SAP does not provide the details of statistical methods for PK analysis, which was developed in a separate analysis plan prior to the primary database lock.

14. QUALITY OF LIFE ANALYSIS

The QoL analyses are addressed in Section 10.4.1. The SAP of the primary CSR has only provided description of main QoL analysis. A detailed statistical analysis of QoL data was provided in a separate HRQoL SAP, which was finalized prior to primary database lock. The HRQoL SAP was appended to the separate specific HRQoL report.

15. GENERAL INFORMATION

There is no interim analysis planned for this study. There are two clinical study reports (CSR) planned: one primary CSR report for marketing authorization application (MAA), and one final CSR report. This SAP will only address the final CSR report.

15.1 Primary CSR

The primary CSR has included safety and efficacy parameters at the time of the primary analysis when all subjects completed 48 weeks of a double-blind Treatment Period or discontinued before reaching 48 weeks, upon which, data base was locked and the study was unblinded. The primary CSR included primary/secondary efficacy endpoints and safety endpoints. The analysis plan for the primary CSR was provided on June 19, 2018.

15.2 Final CSR

[REDACTED] The final analyses will be conducted on the extended secondary efficacy endpoints and safety endpoints. The analysis plan for final CSR is addressed in this SAP.

15.3 DMC

An independent DMC has reviewed the unblinded safety data.

Operational details for the DMC and the algorithm and its validation by an expert panel have been detailed in the DMC charter.

16. IMPACT OF COVID-19 ON EFFICACY AND SAFETY ANALYSIS

The COVID-19 pandemic may impact the conduct and statistical analysis of clinical trials in 3 different aspects (*FDA COVID, 2020; EMA COVID, 2020; ICH E9, 2020; Toshimitsu, 2020; Cro, 2020; Kahan, 2020*):

1. Indirect (operational) impact – quarantine/travel restrictions, site closure, interruption of supply chain to investigational product, overwhelmed healthcare systems, enrollment slow/pause.
2. Direct impact on trial participants - COVID-19 infection, treatment for COVID-19.
3. Impact that may affect endpoint interpretation - delayed/missed visits/assessments, treatment delayed/interrupted/discontinued, study withdrawal, alternative ways of treatment administration, alternative ways of data collection.

Any subjects who had any pandemic-related scenarios mentioned above will be defined as the COVID-19-impacted population in the pandemic period. Any subjects who had contracted COVID-19 will be grouped as the COVID-19-infected population. Therefore, the COVID-19-infected population is a subgroup of the COVID-19-impacted population. The identification of the COVID-19-impacted and COVID-19-infected patients will be conducted on a weekly base and will be finalized prior to the final database lock.

COVID-19 information for the COVID-19-impacted population will be captured in tables of concomitant medication, healthcare resource utilization, summary of dose delay, and protocol deviation. All these 4 tables will have the COVID-19-related fields. The dose delay tables provide the cause of discontinuation due to COVID-19. The protocol deviation table have sections specifying whether the deviations were caused by COVID-19. The table of concomitant medication captures COVID-19 medication if a subject is infected. The healthcare resource utilization table includes the reason for hospitalization caused by COVID-19.

16.1 Sensitivity Analysis of COVID-19 Impact on Efficacy Endpoints

Since the primary and key secondary efficacy analyses have been evaluated before the pandemic in the primary CSR, no sensitivity analyses of COVID-19-impact on the primary and key secondary efficacy endpoints will be conducted.

16.2 Analysis and Reporting of COVID-19 Impact on Safety Endpoints

The summary analyses for safety endpoints will be conducted on COVID-19-infected populations for any adverse events during the entire pandemic period.

Tables summarizing the incidence of TEAEs will be generated for each of the following by treatment group (if not otherwise specified, the summary is by SOC and PT) for COVID-19-infected populations:

- TEAEs;
- Serious TEAE (SAE);
- TEAE with CTCAE Grade ≥ 3 ;
- TEAEs leading to study drug discontinuation.

18. APPENDICES

18.1 Handling of Dates

Dates will be stored as numeric variables in the SAS analysis files and reported in DDMMYYYY format (i.e., the Date9. datetime format in SAS). Dates in the clinical database are classified into the categories of procedure dates, log dates, milestone dates, outcome dates, and special dates.

- **Procedure Dates** are the dates on which given protocol-specified procedure are performed. They include the dates of laboratory testing, physical examinations, tumor scans, etc. They should be present whenever data for a protocol-specified procedure are present and should only be missing when a procedure are marked as NOT DONE in the database. Procedure dates will not be imputed.
- **Log Dates** are dates recorded in eCRF data logs. Specifically, they are the start and end dates for adverse events and concomitant medications/procedures. They should not be missing unless an event or medication is marked as *ongoing* in the database. Otherwise, incomplete log dates will be imputed according to the rules in Appendix 17.2 (e.g., for duration or cycle assignment, etc.). However, in listings, log dates will be shown as recorded without imputation.
- **Milestone Dates** are dates of protocol milestones such as randomization, study drug start date, study drug termination date, study closure date, etc. They should not be missing if the milestone occurs for a subject. They will not be imputed.
- **Special Dates** cannot be classified in any of the above categories and they include the date of birth. They may be subject to variable-specific censoring and imputation rules.

Dates recorded in comment fields will not be imputed or reported in any specific format.

